#### **7.1.8. Withdrawal Due to an Adverse Event**

Any patient who experiences an adverse event may be withdrawn from the study or from study treatment at any time at the discretion of the investigator. If a patient is withdrawn wholly or in part because of an adverse event, both the adverse events page and termination page of the CRF will be completed at that time.

The patient will be monitored at the discretion of the investigator (eg, until the event has resolved or stabilized, until the patient is referred to the care of a health care professional, or until a determination of a cause unrelated to the study drug or study procedure is made). The investigator must inform the medical monitor as soon as possible of all patients who are being considered for withdrawal due to adverse events. Additional reports must be provided when requested.

If a patient is withdrawn from the study or study drug for multiple reasons that include adverse events, the termination page of the CRF should indicate that the withdrawal was related to an adverse event. An exception to this requirement will be the occurrence of an adverse event which in the opinion of the investigator is not severe enough to warrant discontinuation but which requires the use of a prohibited medication, thereby requiring discontinuation of the patient. In

such a case, the reason for discontinuation would be the need to take a prohibited medication, not the adverse event.

A subject should only be designated as lost to follow-up if the site is unable to establish contact with the subject after 3 documented attempts via 2 different methods (phone, text, e-mail, certified letter, etc).

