7.3. Adverse Events

Adverse events will be coded using the Medical Dictionary for Regulatory Activities (MedDRA); the final version number will be indicated in the summary tables.

On-treatment adverse event summaries will be presented by treatment group and overall, based on events with onset during the treatment period. If the AE start date is missing or partial, the event will be considered on-treatment unless there is evidence to the contrary (eg, month and year of AE start is present and is less than the month and year of the first dose of study drug). Post-treatment adverse events with onset during the follow-up period (ie, AE start date greater than the upper bound of the treatment period, as described previously) will be summarized separately.

Summaries will be presented by SOC and/or PT for all adverse events (overall and by severity), adverse events determined by the investigator to be related to study treatment (overall and by severity), serious adverse events, adverse events causing discontinuation from study treatment, and non-serious adverse events. Treatment related adverse event summaries will include events with missing relationship to study drug. For summaries by severity, patients will be counted at the greatest reported severity. Adverse events missing the flag indicating a serious adverse event will be excluded from the summary of serious adverse events, but included in the summary of non-serious adverse events.

In addition, adverse events that begin within 24 hours after study drug injection and injection-site adverse events (as recorded on the CRF) will each be summarized separately.

Summaries for the most common adverse events (incidence $\geq 2\%$ in reslizumab-treated patients) and adverse events occurring with greater frequency for reslizumab-treated patients compared to placebo will also be presented.

All adverse events, including pre-treatment events, will be included in the patient listings. The mapping of MedDRA dictionary terms for adverse event descriptions will also be provided.

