7.3.2. Adverse Events by Subgroup

Overall adverse event categories will be presented for selected subgroups defined in Section 3.4. The categories of adverse events will include:

- Patients with at least one AE
- Patients with at least one treatment-related AE
- Patients with at least one SAE
- Patients with at least one SAE resulting in death
- Patients with at least one AE leading to discontinuation

Selected summaries will also be presented for adverse events by system organ class (SOC), preferred term and subgroup.

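### A missing seriousness flag is counted as non-serious, which can only understate serious adverse events and runs against the SAP's other missing-data defaults

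*SAP*

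**What the plan says.** **Missing flags (SAP 7.3).** On seriousness: "Adverse events missing the flag indicating a serious adverse event will be excluded from the summary of serious adverse events". Such events go to the non-serious table instead. On causality, the same paragraph goes the other way: "Treatment related adverse event summaries will include events with missing relationship to study drug". The paragraph before it treats an event with a missing or partial start date as on-treatment unless something shows otherwise. Protocol 9.7.2 contains the missing-relationship rule but is silent on missing seriousness. The seriousness default is therefore the SAP's own addition, and the SAP gives no reason for it.

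**Discontinuations (Protocol 7.1.8).** If a patient is withdrawn for several reasons and one is an adverse event, "the termination page of the CRF should indicate that the withdrawal was related to an adverse event". There is one exception: an event "which in the opinion of the investigator is not severe enough to warrant discontinuation but which requires the use of a prohibited medication". In that case "the reason for discontinuation would be the need to take a prohibited medication, not the adverse event". SAP 7.3 plans a summary of "adverse events causing discontinuation from study treatment", and SAP 7.3.2 repeats the category by subgroup as "Patients with at least one AE leading to discontinuation". Neither section names the data field behind the table.

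**The concern.** A default for a missing safety field should not resolve uncertainty in the product's favour. Here three fields can be blank, and only the seriousness blank is resolved toward the smaller count. A truly serious event with a blank flag drops out of the serious-event table and appears as non-serious.

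Serious events and discontinuations due to adverse events are the safety figures most readers look at first. They matter more than usual here. Protocol 1.4.1 calls the subcutaneous safety data limited and describes one study, a single 220 mg injection in 45 healthy volunteers.

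The discontinuation rule raises a smaller question of the same kind. If the table takes its events from the termination page, an event that set off the chain leading to a stop may not appear as having caused it.

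**Working it through.** No stated figure rests on either rule, so there is nothing to reproduce. The check is mainly textual, with arithmetic for scale only.

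**1. The three missing-data defaults in SAP 7.3**

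- Relationship missing: counted as related (higher count).
- Start date missing or partial: counted as on-treatment unless contradicted (higher count).
- Seriousness flag missing: counted as non-serious (lower serious-event count).

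**2. Direction of the seriousness default.** Assume that completed flags are correct.

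- Let S be the number of patients in an arm with at least one truly serious event.
- Let m be the number of those patients whose serious events all lack the flag.
- Let f be the number of patients with no truly serious event but at least one event with a blank flag.
- Present rule: reported count = S − m, which never exceeds S.
- Opposite rule: reported count = S + f, which is never below S.

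The present rule can only understate. The opposite rule can overstate, which is why blanks should be resolved before any default is applied.

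**3. Scale.** Inputs are 225 patients per arm (SAP 2.1) and serious-event incidences of 6% on reslizumab and 9% on placebo (Protocol 1.3.2.2, pooled iv studies). That these rates carry over to this trial is an assumption.

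- Expected patients with a serious event: 225 × 0.06 = 13.5 and 225 × 0.09 = 20.25.
- One patient: 100/225 = 0.44 percentage points.
- One patient as a share of the arm's count: 1/13.5 = 7.4% and 1/20.25 = 4.9%.
- If an assumed 1% to 10% of these patients were lost through blank flags, 6% would read 6 × 0.99 = 5.94% to 6 × 0.90 = 5.40%. Likewise 9% would read 9 × 0.99 = 8.91% to 9 × 0.90 = 8.10%.

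**4. The discontinuation table.** Two records could feed it. One is the termination-page reason, governed by Protocol 7.1.8. The other is the action taken regarding study drug, which Protocol 7.1.2 requires for every adverse event.

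- Built from the termination page: events under the exception are absent.
- Built from the action-taken field: they can appear, because that entry belongs to the event and not to the termination reason.

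The SAP does not say which applies, so the effect is possible but not established.

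**5. Protocol sections that do not agree.** Section 7.1.8 treats the need for a prohibited medication as requiring discontinuation. Section 11.1.2 classes use of a prohibited medication as a protocol violation and leaves the sponsor to decide whether the patient stops or continues. Section 3.14 says that, pregnancy aside, there are no formal rules for stopping study drug. Sites could handle and code the same case differently.

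**The case against.** **Few serious events should have a blank flag.** A serious event needs its own form (Protocol 7.1.2) and a report within 24 hours (7.1.5.3.1). Case report forms are checked for completeness and mandatory values (13.2) and approved by the investigator (13.1). This stands and keeps the expected effect small. But Protocol 13.2 does not say that the seriousness flag is mandatory, and neither document describes matching it to the serious adverse event form before tabulation. The data management plan may cover this, but it is not part of the documents.

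**Counting blanks as serious may create a serious event with no form behind it.** This also stands, and it is why reconciliation comes first and the default applies only to what is left.

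**A reader might infer that events vanish from the safety reporting.** The documents do not support that. They remain in the all-event and by-severity summaries, the listings, and any special-interest summary whose terms they meet (SAP 7.3.1). Prohibited-medication stops should also show in disposition by reason for withdrawal (SAP 5.2).

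**A reader might infer that Protocol 7.1.8 strips event-driven stops out of the discontinuation table.** That goes too far. The exception covers only events that the investigator considers not severe enough to warrant stopping. The general rule beside it is conservative, and the table's source is not stated.

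**A reader might infer that the exception catches serious immune or allergic events because immunosuppressants and biologics are prohibited.** No section says so, and the severity condition points the other way. Suspected anaphylaxis has its own form (Protocol 7.1.7.1) and its own summary (SAP 7.3.1.2).

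**Conclusion.** The point on the seriousness flag holds. The default is explicit, can only understate serious adverse events, and is out of step with the other two defaults in its own section. It is a minor point: one affected patient is 0.44 percentage points at 225 per arm, and few are expected. The number of blank flags is not given, so the true effect is unknown. The percentages built on 6% and 9% are illustrations that assume the iv rates apply.

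A reader might infer that the rule favours reslizumab over placebo. The documents do not support that. Each arm's count can only fall, but nothing shows that blank flags would differ between blinded arms, so the between-arm difference could move either way.

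The discontinuation point holds only conditionally: events under the Protocol 7.1.8 exception may be missing if the table is built from the termination page. The firm finding there is that the SAP does not name its source.

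**What to change.** **SAP 7.3, seriousness.** Replace the default with three steps:

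1. Before database lock, query every missing seriousness flag and reconcile it with the serious adverse event forms.
2. Count any event whose flag is still missing as serious.
3. Footnote the serious-event table with the number so counted, by arm.

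**SAP 7.3 and 7.3.2, discontinuations.** State that the table is built from the per-event action-taken field. Alternatively, show stops where an adverse event led to a prohibited medication as a separate row beside the adverse-event discontinuations.

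**Protocol 7.1.8, 11.1.2 and 3.14.** Reconcile what they say about discontinuation after prohibited-medication use. Which rule should apply is a clinical matter for the sponsor.

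**Cost.** The table changes need SAP wording, a footnote and a reconciliation step before lock. They need no new data collection and no Protocol amendment. The serious-event table may look slightly less favourable and may include an event with no serious adverse event form behind it, which the footnote makes visible.

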7.3.1. Adverse Events of Special Interest

7.3.1.1. Administration Site Reactions

Administration site reactions will be defined based on:

- MedDRA HLT: Administration Site Reactions

Summaries will be presented by high level term (HLT), preferred term, and treatment group.

Patients will further be assessed on a 4-point Likert scale (none, mild, moderate, severe) for several domains of localized injection site tolerability including pain, tenderness, erythema, warmth, and swelling. The number and percentage of patients reported for each of the levels will be summarized descriptively for each domain by visit.

7.3.1.2. Anaphylaxis and Hypersensitivity

Anaphylaxis and hypersensitivity events will be defined based on:

- MedDRA SMQ: Anaphylactic Reaction
- MedDRA SMQ: Hypersensitivity

Summaries will be presented separately for both the broad (broad+narrow) and narrow preferred terms by treatment group.

Adverse events suspected by the investigator to be anaphylaxis events will be summarized by preferred term and treatment group. Supplemental information related to the relative timing, clinical manifestation, and treatment of these suspected events will be collected in a dedicated CRF and reported in the patient listings.

7.3.1.3. Malignancies

Malignancies will be defined based on:

- MedDRA SMQ: Malignant Tumors

Summaries will be presented by preferred term and treatment group.

7.3.1.4. Helminth infections

Helminth infections will be defined based on:

- MedDRA HLT: Ectoparasitic Disorders
- MedDRA HLT: Parasite Identification and Serology

- MedDRA HLT: Parasitic Lower Respiratory Tract Infections
- MedDRA HLT: Skin and Subcutaneous Arthropod and Parasitic Infestations

Summaries will be presented by high level term (HLT), preferred term, and treatment group.

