### *Infections*

The immune response to parasitic infections may involve eosinophils; therefore, the clinical course of existing or new parasitic infections could potentially be complicated by a mechanism of action that lowers blood and tissue eosinophils. The iv reslizumab clinical protocols contained an exclusion criterion for patients with active or suspected helminth infestation/infection. The asthma Phase 3 studies were conducted in geographic regions in which helminth infections are prevalent, including South and Central America, Africa, and Asia. There were no helminth infections reported, and no difference was documented between the treatment groups in regards to adverse events that could be associated with gastrointestinal helminth infections.

The overall rate of infection adverse events was lower for reslizumab versus placebo-treated patients, with the types of infection events reported consistent with what would be expected in a primarily adult patient population with an underlying condition of asthma. No potential opportunistic infections were reported.

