#### **7.1.6. Protocol-Defined Adverse Events for Expedited Reporting to Teva**

For the purposes of this protocol, the following are considered protocol-defined adverse events for expedited reporting to Teva: anaphylaxis, newly-diagnosed malignancy, opportunistic infection, and parasitic helminth infection. Protocol-defined adverse events for expedited reporting can be either serious or nonserious according to the criteria outlined in Section 7.1.5.1. The process for reporting a protocol-defined adverse event for expedited reporting is the same as that for reporting a serious adverse event (see Section 7.1.5.3). A list of potential opportunistic infections is found in [Appendix I](#).

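### The SAP's helminth adverse-event search has no group named for helminth or intestinal infection, and does not draw in the cases investigators report under Protocol 7.1.6

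*SAP*

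**What the plan says.** SAP 7.3.1.4 opens with "Helminth infections will be defined based on" and then lists four groups:

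- the first is "MedDRA HLT: Ectoparasitic Disorders";
- the second, for laboratory findings, is "MedDRA HLT: Parasite Identification and Serology";
- the third, for the lung, is "MedDRA HLT: Parasitic Lower Respiratory Tract Infections";
- the fourth, for the skin, is "MedDRA HLT: Skin and Subcutaneous Arthropod and Parasitic Infestations".

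The table is presented by high level term, preferred term and treatment group. The section contains no other criterion and shows no sign of redaction.

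Protocol 7.1.6 names four events for expedited reporting to the sponsor: "anaphylaxis, newly-diagnosed malignancy, opportunistic infection, and parasitic helminth infection". These may be serious or nonserious, and no site of infection is specified. Exclusion criterion n in Protocol 4.2 is likewise not limited by site. In Protocol 1.3.2.2, the text on infections explains that lowering eosinophils could complicate parasitic infection. When it reports the intravenous asthma studies, it refers to "adverse events that could be associated with gastrointestinal helminth infections".

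**The concern.** A special-interest category exists to gather, by arm, the few events that bear on a suspected mechanism. Here the mechanism is eosinophil depletion and the event is helminth infection. The only site the protocol's background mentions for helminth infection is the gut, yet no group in the SAP search is named for it.

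Two errors could follow, in opposite directions. The table could show no helminth infections although an investigator had reported an intestinal one. It could also count, under a helminth heading, events coded to groups named for ectoparasites or arthropods, which are not helminths.

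The first error is the more serious. The protocol already records that no helminth infections were reported in the intravenous asthma Phase 3 studies, which were run partly in regions where such infections are prevalent. A zero in this table would naturally be read as extending that record to subcutaneous dosing. The trial plans about 30 countries, and the regional subgroups in SAP 3.4.5 include Latin America, Asia/Pacific and Middle East/Africa.

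**Working it through.** No arithmetic applies. The check sets the search list beside the events it is meant to find, and then looks for another route into the special-interest section.

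**1. The four groups, by name.**

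| Group in SAP 7.3.1.4 | What the name covers | Named for helminths? | Named for the intestine? |
|---|---|---|---|
| Ectoparasitic disorders | Ectoparasites | No | No |
| Parasite identification and serology | Laboratory findings, any site | No | No |
| Parasitic lower respiratory infections | Lung | No | No |
| Skin and subcutaneous infestations | Skin, including arthropods | No | No |

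Of the four groups, none is named for helminths and none for the intestine. Two (the first and the last) are named for ectoparasites or arthropods.

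**2. The events the protocol asks for.** Protocol 7.1.6 asks for parasitic helminth infection with no site limit. Going by the names, an intestinal infection recorded as a diagnosis matches none of the four groups. It would enter if it were recorded as a laboratory identification or serology finding, or if its term happened to sit under the lung or skin group.

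**3. Other special-interest searches.** The opportunistic-infection list in SAP Table 5 contains no helminth term, so it does not fill the gap.

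**4. Investigator-reported cases.** SAP 7.3.1.2 supplements its MedDRA queries for anaphylaxis with a summary of events the investigator suspected to be anaphylaxis. Helminth infection is on the same expedited list in Protocol 7.1.6, but SAP 7.3.1.4 has no equivalent. A case sent to the sponsor as a parasitic helminth infection could therefore be absent from the table with that title.

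**5. Stated reasons.** The SAP's log of changes for its Amendment 01 says that the special-interest categories and their derivations were added. It gives no reason for choosing these four groups.

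**6. Where a missed case would still appear.** SAP 7.3 tabulates all on-treatment adverse events by system organ class and/or preferred term and by treatment group, tabulates serious events separately, and lists every event. Protocol 7.1.6 sends each case through the serious-event reporting process.

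**The case against.** The strongest objection is that the documents do not reproduce the MedDRA hierarchy, and SAP 7.3 leaves the version to be stated in the tables. Which preferred terms sit under each group cannot be checked here. A reader might infer that the search contains nothing able to catch an intestinal or systemic helminth infection. The documents do not support that: the evidence is the group names, and the serology group is not limited by site. The same limit applies to any statement about which particular ectoparasites would be counted.

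Second, the protocol's wording is broader than the gut. Its background frames the risk as parasitic infection in general, and the gastrointestinal reference comes in a report of past results. The word systemic does not appear there; it can only be inferred from the unrestricted wording of 7.1.6. Because the framing is parasitic, keeping some wider parasite groups is partly defensible, and the quarrel is then with the helminth heading.

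Third, cases are not lost from the study, and few are likely: patients with active or recently treated infection are excluded, and none was reported in the intravenous asthma Phase 3 studies.

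All three points stand as limits on the claim. They do not remove the mismatch between the list and its title, or explain why investigator-reported cases are left out. That omission can be seen without any knowledge of MedDRA.

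**Conclusion.** The point holds as a fault in a stated rule. Followed as written, SAP 7.3.1.4 can leave an investigator-reported intestinal helminth infection out of the table titled for it, and can place events from ectoparasite or arthropod groups in that table.

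The effect is confined to one special-interest summary. A reader might infer that helminth cases would go unreported; they would not, because the general tables, listings and expedited reports still carry them. What would be lost is their grouping by arm under the right heading, and with few events, scattered preferred terms are easy to overlook. No efficacy result or type I error is affected. The number of cases that might be missed cannot be estimated from the documents.

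The conclusion assumes that the group names fairly describe their content. If the sponsor can show that the listed groups already contain the intestinal helminth terms, the coverage part falls away. The missing link to Protocol 7.1.6 and the mixing of ectoparasites with helminths would remain. This should be corrected, but it is not a threat to the trial's main conclusions.

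**What to change.** Before database lock, amend SAP 7.3.1.4 in three ways:

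1. Add to the summary every event the investigator reported as a parasitic helminth infection under Protocol 7.1.6, as SAP 7.3.1.2 does for suspected anaphylaxis. This step does not depend on the MedDRA hierarchy.
2. Extend the search to MedDRA groupings that cover helminth infection at any site, including the intestine, and verify the resulting terms against the version in use.
3. Show ectoparasite and arthropod terms separately from helminth terms.

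The cost is minor programming and a check of the term list. No new data are needed.
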